### 5.3.12. PD biomarkers

Evaluation of PD biomarkers will be performed at the time-points described in Schedule of Study Assessment (Table 5).

The PD activity of SEL24/MEN1703 will be assessed by changes between pre- and post-treatment levels of p-Ser235/6 S6 and other relevant biomarkers as appropriate, in peripheral blood by using flow cytometry.

### 5.3.13. Genetic profile of AML cells

The genetic profile of AML cells will be performed at the time-points described in the Schedule of Study Assessment (Table 5) by using Next Generation Sequencing and/or qRT-PCR. The mutational status of patients before and after treatment with SEL24/MEN1703 will be assessed by the analysis of a panel of relevant AML mutated genes in bone marrow. Left over sample aliquots

and aliquots of bone marrow aspirates/biopsy may be used for future biomarker analysis which is relevant to the development of SEL24/MEN1703 in AML.

Full details of sample collection and handling for these samples will be described in Lab Manual for the study.

#### **5.3.14. PK sampling**

Evaluation of the levels of SEL24/MEN1703 and its metabolites (as appropriate) will be performed at the time-points described in the Schedule of Study Assessment (Table 5). The PK profile of SEL24/MEN1703 and its metabolites, as appropriate, will be evaluated by analysis of concentration levels in plasma. Evaluation of CYP2D6 phenotyping will be carried out (see [Section 5.3.15](#)). Results will be reported separately. In Part 1 ONLY, urine samples will also be collected from the first dose of SEL24/MEN1703 until immediately prior to the second dose for PK analysis.

Nominal PK blood sampling times should be adhered to as closely as possible. It is essential that the actual time and date of collection of each blood sample be recorded in the patient's records and in the eCRF.

Full details of sample collection and handling for these samples will be described in the Lab Manual for the study. Left over sample aliquots could be analyzed for metabolite identification purposes. The results of the metabolite identification analysis will be reported separately.

#### **5.3.15. CYP2D6 phenotyping**

As SEL24/MEN1703 may both inhibit and act as a substrate for Cytochrome P450 enzyme CYP2D6, patients will be assessed for their CYP2D6 phenotype. A blood sample collected during Screening will be used for this assessment.

#### **5.3.16. CD25 Expression**

An aliquot of PD sample collected during Screening will be used for this assessment.

#### **5.3.17. Mutational Status**

AML mutational status will be assessed locally at Screening.

#### **5.3.18. AML Karyotypic Analysis**

AML Karyotype analysis will be performed locally at Screening.

#### **5.3.19. Transfusion Status**

Need for blood transfusion will be recorded as concomitant medication during patient participation to the study. In particular, information on blood transfusion occurred from 28 days prior to the first dose of SEL24/MEN1703 to the Final Study Visit will be collected to define transfusion conversion rate and transfusion maintenance rate.

Transfusion status (independent Vs. dependent) at baseline period and post-baseline period are defined as follows for subjects who took at least one dose of study drug:

Baseline transfusion status:

- Baseline period is defined as the period from 28 days prior to the first dose to 28 days post first dose (C2D7). For subjects who are on treatment <28 days, baseline period is from 28 days prior to the first dose (in the event that this information is not available the ICF signature date will be exploited) until the end of treatment.
- Subjects are classified as baseline transfusion independent if there is no red blood cells (RBC) or platelet transfusions within the baseline period; otherwise, the subject is to be considered as baseline transfusion dependent.

Post-baseline transfusion status:

- Post-baseline period is defined as the period from 29 days post first dose (day after C2D7) until last dose.
- For subjects who are on treatment  $\geq 84$  days (C5D1 or more), subjects are classified post-baseline transfusion independent in the event of 56 consecutive days without any RBC or platelet transfusion within post-baseline period
- For subjects who are on treatment  $>28$  days (C2D7) but  $<84$  days (C4D21), post-baseline transfusion status is not evaluable
- Otherwise, the subject is considered post-baseline transfusion dependent.

Both transfusion conversion rate and maintenance rate apply to subjects who have evaluable post-baseline transfusion status.

Transfusion conversion rate is defined as the number of subjects who were transfusion dependent at baseline period but become transfusion independent at post-baseline period divided by the total number of subjects who were transfusion dependent at baseline period. Transfusion maintenance rate is defined as the number of subjects who were transfusion independent at baseline period and still maintain transfusion independent at post-baseline period divided by the total number of subjects who were transfusion independent at baseline period.

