***Transfusion conversion rate and transfusion maintenance rate***

Starting from Protocol V12.0, information about transfusion dependency will be collected and evaluated among study endpoints. For the purpose of defining transfusion conversion rate and transfusion maintenance rate, transfusion status (independent Vs. dependent) at baseline period and post-baseline period are defined as follows for subjects who took at least one dose of study drug:

Baseline transfusion status:

- Baseline period is defined as the period from 28 days prior to the first dose to 28 days post first dose (C2D7). For subjects who are on treatment <28 days, baseline period is from 28 days prior to the first dose (in the event that this information is not available the ICF signature date will be exploited as baseline period start) until the end of treatment.
- Subjects are classified as baseline transfusion independent if there is no red blood cells (RBC) or platelet transfusions within the baseline period; otherwise, the subject is to be considered as baseline transfusion dependent.

Post-baseline transfusion status:

- Post-baseline period is defined as the period from 29 days post first dose (day after C2D7) until last dose.
- For subjects who are on treatment  $\geq 84$  days (C5D1 or more), subjects are classified post-baseline transfusion independent if there is one consecutive 56 days period without any RBC or platelet transfusion in the post-baseline period.
- For subjects who are on treatment  $>28$  days (beyond C2D7) but  $<84$  days (up to C4D21), post-baseline transfusion status is not evaluable.
- Otherwise, the subject is considered post-baseline transfusion dependent.

Both transfusion conversion rate and maintenance rate apply to subjects who have evaluable post-baseline transfusion status.

Transfusion conversion rate is defined as the number of subjects who were transfusion dependent at baseline period but become transfusion independent at post-baseline period divided by the total number of subjects who were transfusion dependent at baseline period. Transfusion maintenance rate is defined as the number of subjects who were transfusion independent at baseline period and still maintain transfusion independent at post-baseline period divided by the total number of subjects who were transfusion independent at baseline period.

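### Read literally, the post-baseline transfusion rule counts patients treated 28 days or less as failures but drops those treated more than 28 and fewer than 84 days

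*Protocol*

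**What the plan says.** Protocol 5.3.19, and the matching synopsis section, define transfusion status for everyone who took at least one dose.

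- **Baseline.** The period covers 28 days either side of first dose. Short treatment is provided for: "For subjects who are on treatment <28 days, baseline period is from 28 days prior to the first dose" to the end of treatment.
- **Post-baseline period.** "Post-baseline period is defined as the period from 29 days post first dose (day after C2D7) until last dose".
- **84 days or more.** For patients on treatment at least 84 "days (C5D1 or more), subjects are classified post-baseline transfusion independent in the event of 56 consecutive days" free of red cell and platelet transfusion.
- **More than 28 but fewer than 84 days.** Here "post-baseline transfusion status is not evaluable".
- **Everyone else.** "Otherwise, the subject is considered post-baseline transfusion dependent".
- **Denominators.** "Both transfusion conversion rate and maintenance rate apply to subjects who have evaluable post-baseline transfusion status".

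SAP 5.4.2 repeats the two formulas and the restriction to evaluable patients, but does not define the statuses. SAP 3.1 says the analyses follow the protocol. SAP 12.1 limits both rates to the IDH-mutant cohort (about 20 planned), computes them on the safety and efficacy populations, and plans no formal testing.

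**The concern.** No line gives a post-baseline status to patients treated 28 days or less, so they fall into the residual clause. They are labelled dependent over a period containing no days. Patients who last a little longer do have some post-baseline days, possibly with transfusions in them, and they are removed. The evident reason for removal is too little follow-up to show 56 transfusion-free days. That reason applies even more strongly to the group that is kept and counted as failing.

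With the same number of successes, both rates then depend on when the other patients happen to stop. Stopping by day 28 lowers the rate; stopping between day 29 and day 83 leaves it untouched. In a cohort of about 20, a few patients on one side or the other of day 28 can move the reported percentage substantially.

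**Working it through.** The documents give no expected rate or sample size for these endpoints, so there is no stated figure to reproduce. The check applies the rule as written and then illustrates its effect.

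**1. Classification by time on treatment.** Count first dose as day 1 and let t be the day of last dose. Post-baseline days = max(0, t − 28). With 14 dosing days in each 21-day cycle and no delays, last doses of cycles 1 to 5 fall on days 14, 35, 56, 77 and 98.

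| t | Post-baseline days | Status under the rule | In denominator? |
|---|---|---|---|
| 14 | 0 | dependent | yes, as failure |
| 28 | 0 | dependent | yes, as failure |
| 29 | 1 | not evaluable | no |
| 35 | 7 | not evaluable | no |
| 56 | 28 | not evaluable | no |
| 77 | 49 | not evaluable | no |
| 83 | 55 | not evaluable | no |
| 84 | 56 | independent or dependent | yes |
| 98 | 70 | independent or dependent | yes |

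So a patient who stops after cycle 1 is a failure, and one who stops after completing the dosing of cycle 2, 3 or 4 is dropped.

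**2. The maintenance case.** A patient stops on day 14 with no transfusion from 28 days before first dose to the end of treatment. The patient is baseline independent, becomes post-baseline dependent under the residual clause, and counts as a maintenance failure. A baseline-independent patient who stops on day 35 and was transfused on day 30 leaves the maintenance denominator.

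**3. Direction.** Let x be successes, n84 the patients treated 84 days or more, k those treated 28 days or less, and m those in between, with N = n84 + k + m. Starting at day 29, the middle group has at most 83 − 29 + 1 = 55 post-baseline days, one short of 56, so it contains no success. The rate as written is x/(n84 + k). The rate over all dosed patients is x/N. Since m ≥ 0, the first equals or exceeds the second.

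There is one edge case. If first dose is day 0 and the period starts at the visit label (the day after C2D7, then day 28), a last dose on day 83 leaves 83 − 28 + 1 = 56 days.

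**4. Size, on assumed counts.** Conversion, with N = 16 baseline-dependent, n84 = 4 and x = 2:

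| k | Rule as written, 2/(4 + k) | All dosed, 2/16 |
|---|---|---|
| 0 | 50% | 12.5% |
| 3 | 28.6% | 12.5% |
| 6 | 20% | 12.5% |
| 9 | 15.4% | 12.5% |
| 12 | 12.5% | 12.5% |

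With n84 = 8 and x = 4, the rule gives 4/8 = 50% at k = 0 and 4/16 = 25% at k = 8, against 25% over all dosed.

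Maintenance, with N = 4 baseline-independent, n84 = 2 and x = 1: the rule gives 1/2 = 50%, 1/3 = 33.3% and 1/4 = 25% for k = 0, 1 and 2, against 25% over all dosed.

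Exact 95% intervals are wide and overlap: 2/16 gives 1.6–38.3%, 2/10 gives 2.5–55.6%, and 2/4 gives 6.8–93.2%.

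**5. Does the efficacy population remove the problem?** No. SAP 7.3 keeps anyone who completes the 21 days of cycle 1 with at least 75% of the drug. A patient who then stops had a last dose on about day 14 and is still in the failing group.

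**The case against.** The best defence is that each half of the rule can be justified. Counting very early stoppers as conversion failures is conservative, and excluding patients too short on treatment to show 56 clear days is sensible. The residual clause may also have been meant only for patients treated 84 days or more without a 56-day run. The first argument does not explain why the shorter-treated group is the one kept, and it does not rescue the maintenance rate. The second may well be the intent, but the text does not say it.

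Four stronger readings are tempting and should not be adopted.

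- **The SAP already points to dropping the early group.** A reader might infer this from the non-missing counts in SAP 11.2 and the observed-cases rule in SAP 11.3. Both concern missing values. A status assigned by the residual clause is not missing, and SAP 3.1 keeps the protocol rule.
- **The dropped group can never succeed under any day count.** This holds from the numeric start of 29 days, but not in the one-day edge case above.
- **The visit labels make the cut-offs unworkable.** With first dose as day 1, C2D7 is day 28, C4D21 is day 84 and C5D1 is day 85; with first dose as day 0 they are 27, 83 and 84. Neither count fits all three labels, but the labels are in parentheses and the numeric limits can govern. Time on treatment has no explicit definition, yet the post-baseline period ends at last dose, and Protocol 8.6 summarises administration up to the last treatment received.
- **The formulas contradict the restriction to evaluable patients.** They divide by a total number, but the evaluable-only sentence limits that total. This is loose drafting.

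**Conclusion.** The inconsistency is in the protocol text as written, and the SAP does not correct it. The certain part is the classification: zero post-baseline days counts as failure, while 1 to 55 post-baseline days means exclusion. It also follows, from the numeric day-29 start, that the evaluable-only rate cannot fall below the all-dosed rate.

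The size is not known. The range from 50% to 12.5% rests entirely on assumed counts and shows sensitivity, not bias in this trial. Both endpoints are descriptive and secondary, sit in one cohort of about 20, and feed no decision rule; the Part 2 primary objective is safety. Importance is minor to moderate. It is still worth correcting, because the rule as stated gives a wrong answer for the never-transfused early stopper and the correction is cheap.

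**What to change.** In SAP 5.4.2 and 12.1, before database lock:

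1. Apply one rule to everyone who stops before day 84. Classify patients treated 28 days or less as not evaluable, like the group treated more than 28 but fewer than 84 days. Limit the residual clause to patients treated 84 days or more without a 56-day transfusion-free run. Record this in SAP 3.1 as a change from the protocol.
2. Beside it, report each rate over all dosed baseline-dependent (or baseline-independent) IDH-mutant patients, counting anyone without a documented 56-day post-baseline run as not achieved. Note that for maintenance this includes early stoppers who were never transfused. The companion is needed because step 1 alone gives the favourable end of the range: 2/4 = 50% for every k in the conversion example.
3. By baseline status, give the numbers treated 28 days or less, more than 28 but fewer than 84 days, and 84 days or more, with the number in the middle group transfused after baseline.
4. As a minor clarification, state that time on treatment runs from first to last dose and that the numeric cut-offs take precedence over the visit labels.

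The cost is SAP wording, a recorded departure from the protocol's literal rule, and a few table rows. No new data are needed: transfusions are collected from 28 days before first dose to the Final Study Visit, and treatment intake is already listed. The companion rate may look less favourable.

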## 6. STUDY MEDICATION AND ADMINISTRATION

The Quality Control Standards and requirements for SEL24/MEN1703 study medication are described in separate release protocols/Certificate of Analysis.

SEL24/MEN1703 IMP will be supplied as gelatin capsules containing 25 and 100 mg SEL24/MEN1703 API (free base) (not-formulated API in capsule) and gelatin capsules containing 25 and 100 mg API (free base) as formulated drug product (formulated drug product in capsule), respectively. Details of the Investigational Product provided during Part 1 are reported in Table 3. Formulated drug only will be provided for Part 2.

The drug product used until the implementation of protocol amendment V8.0 is API directly filled by weight in capsules, which is a suitable procedure for small scale batches in early development stages. However, this formulation and manufacturing process are not suitable for later clinical phases and for industrial scale production for commercial purposes. Therefore, a formulation of drug product has been developed to guarantee a standardized manufacturing process.

**Table 12: Composition of SEL24/MEN1703 for oral use**

Active components	25 mg capsules: 25 mg SEL24/MEN1703 (free base) 100 mg capsules: 100 mg SEL24/MEN1703 (free base)
Excipients	[REDACTED]
Stability	Stability testing of SEL24/MEN1703 is on-going and the IMP shelf-life will be extended as appropriate during the course of the clinical study
Storage and handling	API in capsules: SEL24/MEN1703 IMP (API in capsules) must be stored at controlled room temperature [20-25 °C (68-77 °F)]. The bottles should be stored protected from light Formulated drug product in capsules: Do not store the SEL24/MEN1703 IMP (formulated drug product in capsules) above 25 °C (77 °F). Do not freeze. Store in the original package

Please refer to the current version of the IB for additional information on the physical, chemical and pharmaceutical properties of SEL24/MEN1703.

### 6.1. Labeling of SEL24/MEN1703

The IMP SEL24/MEN1703 will be labelled in compliance with the current valid international and corresponding national requirements. The label will report instructions on how to administer and store the SEL24/MEN1703 IMP in local language of the respective study country.

### 6.2. SEL24/MEN1703 Starting Dose and Duration of Treatment on Study

The starting dose of SEL24/MEN1703 will be 25 mg, taken orally once daily for 14 consecutive days over a 21-day treatment cycle. The cohort dose may be escalated by an increase in the daily dose level during the study based on the dose escalation rules.

Reasons for withdrawal from the study and SEL24/MEN1703 treatment are described in [Section 3.4](#).

Continuation of the study treatment may be discussed between the Investigator and the Sponsor on a case-by-case basis. The DMC may also advise on the suitability of an individual patient to continue to receive study treatment.

Patients who experience a DLT will be permitted to receive further treatment with SEL24/MEN1703 according to the dose modification rules described in [Section 4.4](#).

### **6.3. Storage of SEL24/MEN1703**

SEL24/MEN1703 will be shipped to the site and must be stored at the site in a secure location under controlled room temperature conditions. Do not store SEL24/MEN1703 IMP (formulated drug product in capsules) above 25 °C (77 °F).

Detailed instructions for the storage of dispensed IMP at home will be provided to every patient enrolled in the clinical study.

### **6.4. Blinding and Procedures for Un-blinding the Study**

This is an open-label study, and there are no procedures for blinding and un-blinding.

### **6.5. Provision and Replacement of SEL24/MEN1703**

Sufficient doses of SEL24/MEN1703 medication will be supplied. Where clinical supplies (or packaging) are apparently damaged on receipt or considered unfit for use by the study site, the Sponsor (or their delegate) must be notified immediately. Where required, clinical study supplies will be replaced. Further details on the handling of SEL24/MEN1703 at site will be described in the Pharmacy Manual.

### **6.6. Drug Accountability**

The Investigator is obliged to keep sufficient documentation of the delivery, use and destruction or return of unused, used or partially used IMP. The documentation must include dates, quantities, patient numbers, batch numbers or other identification number. The Investigator may assign some or all of the Investigator's duties for drug accountability to an appropriate pharmacist. Roles and responsibilities of site staff will be recorded in the Investigator Site File.

The Investigator should maintain records that document adequately that the patients have been administered the doses specified in the protocol and reconcile all SEL24/MEN1703 received for the study. The local study monitor will be responsible for checking the drug accountability records maintained by the site during the monitoring visits.

The medication provided for this study is for use only as directed in the protocol. It is the Investigator and their institution's responsibility to establish a system for handling study drug so as to ensure that:

- deliveries of SEL24/MEN1703 are correctly received by a responsible person;

- such deliveries are recorded;
- study treatments are handled and stored safely and properly as stated on the label;
- study drug is only dispensed to study patients in accordance with the protocol; and
- any unused study drug is destroyed locally or returned for destruction in liaison with the study monitor.

Throughout the study, it must be possible to reconcile delivery records with records of usage and any destroyed/returned stock of SEL24/MEN1703. To help with compliance checks, records of usage should include the identification of the patient to whom the study treatment was dispensed and the quantity and date of dispensing, plus all unused supplies at the end of each treatment cycle. Patients will be asked to maintain a dosing diary and bring it with them to study visits to support reconciliation and compliance checks. This record is in addition to any drug accountability information recorded on the eCRF. Any discrepancies must be accounted for on the appropriate forms. Certificates of delivery and return must be signed by the responsible pharmacist, and copies retained in the Pharmacy File.

The return or destruction of unused drug will be conducted after written approval by the Sponsor, with appropriate documentation and drug accountability procedures completed following destruction.

### **6.7. Treatment Allocation**

In order to ensure that the appropriate numbers of patients are enrolled to each cohort in Part 1 and in Part 2, and that enrolment to the study is appropriately controlled, on identifying a potential study patient, the Investigator is required to register a patient in the study. Patients will be registered in the study by using the Interactive Web Response System (IWRS) automated patient registration system (see the Study Operations Manual for specific instructions).

Prior to registration of Screening in IWRS and any study-specific evaluations being performed, all patients must have given written informed consent for the study. Patients must have completed the Screening evaluations and must meet all of the eligibility requirements listed in [Section 3](#) prior to being registered in the system as enrolled. Study drug will be assigned through the IWRS.

There will be regular communication with the sites during the study, in addition to the Cohort Review Meetings to ensure that Investigators are aware of enrolment status on the study and of suitable times for patient enrolment.

